

NAME OF COMPANY: Travere Therapeutics, Inc.
	
NAME OF FINISHED PRODUCT: sparsentan tablets

STATISTICAL METHODS:
 
Power and Sample Size:
 
Approximately 300 patients will be randomized and allocated 1:1 to receive sparsentan or irbesartan. This sample size takes into consideration enrollment feasibility in this rare disease setting and was evaluated using simulations.
 
For the surrogate endpoint, at the time of the interim analysis (which is planned for after 36 weeks following randomization of at least 190 patients [approximately 95 per treatment group]), the power to detect a difference in response proportions between treatment groups is more than 90%, assuming the response proportions are 50% for sparsentan and 20% for irbesartan, with a 2-sided α of 0.05.
 
For the primary endpoint (slope of eGFR) at the final analysis, the study has at least 90% power to differentiate between treatments if the underlying eGFR slope difference is at least 2.5 mL/min/1.73 m² per year for the chronic slope over 2 years (non-US) or at least 2.1 mL/min/1.73 m² per year for the total slope over 2 years (US). The calculations assume that the separate tests for US and non-US countries are performed at a 2-sided α of 0.05 and that statistically significant difference is demonstrated at the interim analysis of the surrogate endpoint.
 
Analysis Sets:
 
Full Analysis Set (FAS): All patients who are randomized and take at least 1 dose of double-blind study medication will be included in the FAS. All analyses of the FAS will be based on each patient's randomized assigned treatment. If a patient is incorrectly stratified (ie, randomized according to the incorrect stratification), the patient will be analyzed under the randomized treatment for the stratum recorded in the randomization system. All efficacy analyses for the double-blind period will be based on the FAS.
 
Per Protocol (PP) Analysis Set: The PP Analysis Set will include all patients in the FAS who meet the study eligibility requirements and have no major protocol deviations that affect the validity of the efficacy measurements. Patients will be analyzed according to their randomized treatment. The PP Analysis Set will be used for a sensitivity analysis of the primary efficacy endpoint. The criteria for inclusion in the PP Analysis Set will be finalized prior to study unblinding and detailed in the Statistical Analysis Plan.
 
Safety Analysis Set: All patients who are randomized and take at least 1 dose of double-blind study medication will be included in the Safety Analysis Set. Safety analyses will be based on randomized treatment.
 
Open-Label Extension Full Analysis Set (OLEFAS): All patients who received at least 1 dose of open-label sparsentan in the open-label extension will be included in the OLEFAS. All efficacy and safety analyses during the open-label extension will be based on the OLEFAS.
 
Demographics and Baseline Characteristics:
 
Demographic data and baseline characteristics for the FAS, PP, and Safety Analysis Sets will be summarized by treatment group using descriptive statistics. Demographic data include sex, age (years), categorical age (<18 years and ≥18 years), race/ethnicity, weight (kg), height (cm), and calculated BMI. Baseline characteristics also include reproductive status (for females only), HbA1c, baseline eGFR, and current use of: steroids, calcineurin inhibitors, mycophenolate mofetil and other immunosuppressive agents, RAAS inhibitors (ie, angiotensin-converting enzyme inhibitors, ARBs, aldosterone blockers, and aliskiren) prior to the 2-week washout, diuretics, additional antihypertensive treatments, and statins.
 
Likewise, demographic data and baseline characteristics for the OLEFAS will be summarized overall using descriptive statistics.
 
Efficacy:
 
All efficacy analyses during the double-blind period will be performed based on the FAS. The primary endpoint analysis will also be conducted using the PP Analysis Set.
	

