
NAME OF COMPANY: Travere Therapeutics, Inc.	NAME OF FINISHED PRODUCT: sparsentan tablets

The eGFR during the screening period will be determined using the Chronic Kidney Disease Epidemiology (CKD-EPI) equation for adults (Levey 2009) and the Modified Schwartz formula (Schwartz 2009a; Schwartz 2009b) for children <18 years of age.
 
The eGFR for each timepoint (visit) during the double-blind period will be determined using the CKD-EPI equation for adults (Levey 2009) and children ≥ 16 years of age at screening for the double-blind period, and the Modified Schwartz formula for children <16 years of age at screening for the double-blind period (Schwartz 2009a; Schwartz 2009b). For the double-blind period, UP/C will be determined using first morning void urine samples and will be calculated as the average of 3 first morning void urine samples collected within 5 days prior to each visit at which UP/C is assessed.
 
The eGFR for each timepoint (visit) during the open-label extension will be determined using the CKD-EPI equation for adults (Levey 2009) and children ≥ 16 years of age at Week 108, and the Modified Schwartz formula for children <16 years of age at Week 108 (Schwartz 2009a; Schwartz 2009b). For the open-label extension, UP/C will be determined using 1 first morning void sample collected within 5 days prior to each visit at which UP/C is assessed.
 
As UP/C is a highly-skewed variable, analyses will be performed on log-transformed data; however, for ease of interpretation, results will be presented in the original units.
 
To control the overall type I error for this study when conducting significance tests for the primary and secondary efficacy endpoints, a hierarchical (gate-keeping) testing procedure will be used.
 
The surrogate efficacy endpoint (UP/C response at Week 36) will first be tested at the interim analysis at 2-sided $\alpha = 0.05$. If the test is not significant, hypothesis testing stops. If the test is significant, then the following country-specific hierarchical testing will be performed.
 
For non-US countries, the hierarchy for the hypothesis testing will be as follows, if the test of the surrogate efficacy endpoint (UP/C response at Week 36) is significant:
 
 test the primary efficacy endpoint (eGFR chronic slope over 2 years) at the final analysis at 2-sided $\alpha = 0.05$. If the test is not significant, hypothesis testing stops. If the test is significant, test the 3 secondary efficacy endpoints using a Bonferroni-Holm procedure to control for family-wise error rate at 2-sided $\alpha = 0.05$. 
For the US, the hierarchy for the hypothesis testing will be as follows, if the test of the surrogate efficacy endpoint (UP/C response at Week 36) is significant:
 
 test the primary efficacy endpoint (eGFR total slope over 2 years) at the final analysis at 2-sided $\alpha = 0.05$. If the test is not significant, hypothesis testing stops. If the test is significant, test the efficacy endpoint of eGFR chronic slope over 2 years at the final analysis at 2-sided $\alpha = 0.05$. If the test is not significant, hypothesis testing stops. If the test is significant, test the efficacy endpoint of change in eGFR from baseline of the double-blind period to 4 weeks post-cessation of randomized treatment at Week 112 at the final analysis at 2-sided $\alpha = 0.05$. 
For the primary endpoint of slope of eGFR evaluated following the initial acute effect of randomized treatment (ie, from Week 6 to Week 108; chronic slope over 2 years), a mixed-effects model with linear spline (knot or change point at Week 6) will be fitted to the available eGFR data. The response variable is the eGFR measured at post-baseline assessments for each patient during the double-blind period. The model will include fixed effects for treatment, both stratification factors for randomization, baseline eGFR (continuous), time (in weeks) from baseline (continuous), and time (in weeks) from the change point (ie, $\text{timek} = \max(\text{time} - 6, 0)$), time-by-treatment, and timek-by-treatment interactions. The model will also include a random intercept and random slopes (time and timek) for each patient. The mixed model will utilize restricted maximum likelihood estimation with Kenward-Roger method used to compute the denominator degrees of freedom for tests of fixed effects. The model will assume an unstructured covariance matrix. If the model does not converge under the unstructured covariance matrix, the autoregressive-1 covariance structure will be used. The primary efficacy
	

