12.10.2. Multiple Comparisons/Multiplicity

To control the overall type I error for this study when conducting significance tests for the primary and secondary efficacy endpoints, a hierarchical (gate-keeping) testing procedure will be used.

The surrogate efficacy endpoint (UP/C response at Week 36) will first be tested at the interim analysis at 2-sided $\alpha = 0.05$. If the test is not significant, hypothesis testing stops. If the test is significant, then the following country-specific hierarchical testing will be performed.

For non-US countries, the hierarchy for the hypothesis testing will be as follows, if the test of the surrogate efficacy endpoint (UP/C response at Week 36) is significant:

1. test the primary efficacy endpoint (eGFR chronic slope over 2 years) at the final analysis at 2-sided $\alpha = 0.05$. If the test is not significant, hypothesis testing stops. If the test is significant,
2. test the 3 secondary endpoints using a Bonferroni-Holm procedure to control for family-wise error rate at 2-sided $\alpha = 0.05$.

For the US, the hierarchy for the hypothesis testing will be as follows, if the test of the surrogate efficacy endpoint (UP/C response at Week 36) is significant:

1. test the primary efficacy endpoint (eGFR total slope over 2 years) at the final analysis at 2-sided $\alpha = 0.05$. If the test is not significant, hypothesis testing stops. If the test is significant,
2. test the efficacy endpoint of eGFR chronic slope over 2 years at the final analysis at 2-sided $\alpha = 0.05$. If the test is not significant, hypothesis testing stops. If the test is significant,
3. test the efficacy endpoint of change in eGFR from baseline of the double-blind period to 4 weeks post-cessation of randomized treatment at Week 112 at the final analysis at 2-sided $\alpha = 0.05$.

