8.2. Statement of the Null and Alternative Hypotheses

The final analysis of the primary endpoint in non-US countries will test the following hypothesis using the FAS:

- H_0 : Slope of eGFR over the blinded treatment period (after adjusting for early hemodynamic effects) is equal between sparsentan and irbesartan
- H_1 : Slope of eGFR over the blinded treatment period (after adjusting for early hemodynamic effects) is different between sparsentan and irbesartan

The final analysis of the primary endpoint in the US will test the following hypothesis using the FAS:

- H_0 : Slope of eGFR over the blinded treatment period is equal between sparsentan and irbesartan
- H_1 : Slope of eGFR over the blinded treatment period is different between sparsentan and irbesartan

The interim analysis of the surrogate endpoint at Week 36 will test the following hypothesis using the IAS:

- H_0 : Proportion of patients achieving FPPE at Week 36 is equal between sparsentan and irbesartan

- H₁: Proportion of patients achieving FPRE at Week 36 is different between sparsentan and irbesartan

The final analysis of secondary efficacy endpoints in non-US countries will test the following hypotheses using the FAS:

- H₀₁: Percent change from Week 6 in eGFR at Week 108 is equal between sparsentan and irbesartan
- H₁₁: Percent change from Week 6 in eGFR at Week 108 is different between sparsentan and irbesartan
- H₀₂: Percent change in eGFR from baseline to 4 weeks post-cessation of randomized treatment at Week 112 is equal between sparsentan and irbesartan
- H₁₂: Percent change in eGFR from baseline to 4 weeks post-cessation of randomized treatment at Week 112 is different between sparsentan and irbesartan
- H₀₃: Slope of eGFR over the blinded treatment period is equal between sparsentan and irbesartan
- H₁₃: Slope of eGFR over the blinded treatment period is different between sparsentan and irbesartan

The final analysis of secondary efficacy endpoints in the US will test the following hypotheses using the FAS:

- H₀₁: Slope of eGFR over the blinded treatment period (after adjusting for early hemodynamic effects) is equal between sparsentan and irbesartan
- H₁₁: Slope of eGFR over the blinded treatment period (after adjusting for early hemodynamic effects) is different between sparsentan and irbesartan
- H₀₂: Change in eGFR from baseline to 4 weeks post-cessation of randomized treatment at Week 112 is equal between sparsentan and irbesartan

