8.4. Multiple Comparisons and Multiplicity

The overall family-wise Type I error rate will be controlled by a hierarchical (gatekeeping) testing procedure.

The surrogate efficacy endpoint (UP/C response at Week 36) will first be tested at the interim analysis at 2-sided $\alpha = 0.05$. If the test is not significant, hypothesis testing stops. If the test is significant, then the following country-specific hierarchical testing will be performed.

For non-US countries, the hierarchy for the hypothesis testing will be as follows, if the test of the surrogate efficacy endpoint (UP/C response at Week 36) is significant:

1. test the primary efficacy endpoint (eGFR chronic slope over 2 years) at the final analysis at 2-sided $\alpha = 0.05$. If the test is not significant, hypothesis testing stops. If the test is significant,

2. test the 3 secondary endpoints using a Bonferroni-Holm procedure to control for family-wise error rate at 2-sided $\alpha = 0.05$.

For the US, the hierarchy for the hypothesis testing will be as follows, if the test of the surrogate efficacy endpoint (UP/C response at Week 36) is significant:

1. test the primary efficacy endpoint (eGFR total slope over 2 years) at the final analysis at 2-sided $\alpha = 0.05$. If the test is not significant, hypothesis testing stops. If the test is significant,
2. test the efficacy endpoint of eGFR chronic slope over 2 years at the final analysis at 2-sided $\alpha = 0.05$. If the test is not significant, hypothesis testing stops. If the test is significant,
3. test the efficacy endpoint of change in eGFR from baseline of the double-blind period to 4 weeks post-cessation of randomized treatment at Week 112 at the final analysis at 2-sided $\alpha = 0.05$.

For planned statistical tests that are not formally performed as a result of the aforementioned multiplicity adjustment strategy, nominal 2-sided p-values (without adjustment for multiplicity) will be computed as a measure of the strength of association between the endpoint and the treatment effect rather than formal tests of hypothesis.

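### The testing plan claims study-wide type I error control, but two regional hierarchies each use the full 0.05 on the same patients, so error is controlled within each hierarchy and not across the two

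*Protocol*

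**What the plan says.** The protocol gives the purpose of the procedure as "To control the overall type I error for this study when conducting significance tests for the primary and secondary efficacy endpoints" (synopsis, repeated in 12.10.2). SAP 8.4 opens with: "The overall family-wise Type I error rate will be controlled by a hierarchical (gatekeeping) testing procedure". Neither sentence is limited to a region.

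The procedure, identical in both documents, is:

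- **Gate.** UP/C response at Week 36 is tested at the interim analysis at 2-sided 0.05. If it fails, all testing stops.
- **Non-US hierarchy.** Chronic slope (Week 6 to 108) at 0.05, then three secondaries by Bonferroni-Holm at 0.05: percent change in eGFR from Week 6 to Week 108, percent change from baseline to Week 112, and total slope.
- **US hierarchy.** Total slope (Day 1 to Week 108) at 0.05, then chronic slope at 0.05, then change in eGFR to Week 112 at 0.05.

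The synopsis confirms that alpha is not divided: "The calculations assume that the separate tests for US and non-US countries are performed at a 2-sided α of 0.05". The regions are not different patients. SAP 8.2 says: "The final analysis of the primary endpoint in the US will test the following hypothesis using the FAS". It puts the non-US primary on the same set, which SAP 6.3.1 defines as everyone randomised and dosed. The power statements for both primaries in SAP 4.3.1.2 use the same 300 patients.

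**The concern.** A claim of overall family-wise control means that the chance of any false rejection is at most 5% whichever hypotheses happen to be true. A single fixed sequence behind a gate has that property. Here the sequence splits in two after the gate. Each branch begins with its own primary at the full 0.05, and failure in one branch does not stop the other. Once the gate is open, there are two routes to a false primary claim, by tests that are correlated but not identical.

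The case that matters is a real proteinuria effect with no effect on slope. Protocol 4.3 treats the step from reduced proteinuria to preserved kidney function as a hypothesis still to be investigated, so the final analysis must guard against exactly that case. What is at stake is the accuracy of a stated error property that will be carried into the study report.

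**Working it through.** **Inputs.** From the documents: the three alpha levels of 0.05; one Full Analysis Set of about 300 patients, 150 per arm; total-slope difference 2.1 and SD 5.50 mL/min/1.73 m² per year (protocol 12.2.2); surrogate response 50% versus 20% with 95 per arm (12.2.1). Assumed, because the documents give no value: the correlation ρ between the two slope test statistics.

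**Plan's own figures.** Total slope: SE = 5.50 × √(2/150) = 0.635 and 2.1/0.635 = 3.307. Power = Φ(3.307 − 1.960) = 91.1%, which reproduces the stated minimum of 90% at an undivided 0.05. Surrogate: (0.30 − 1.960 × 0.0692)/0.0657 = 2.50, so power is 99.4%, consistent with the stated figure of more than 90%. If the assumed surrogate effect is real, the gate is almost always open. Neither document prints a numerical study-wise error rate.

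**Error rate with the gate open and both slopes null.** With Z₁ and Z₂ standard bivariate normal with correlation ρ,

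P(at least one false primary) = 0.05 + 0.05 − P(|Z₁| > 1.96 and |Z₂| > 1.96).

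| ρ (assumed) | P(both) | P(at least one) |
|---|---|---|
| 0.99 | 4.34% | 5.66% |
| 0.97 | 3.87% | 6.13% |
| 0.95 | 3.54% | 6.46% |
| 0.90 | 2.96% | 7.04% |
| 0 | 0.25% | 9.75% |

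The rate equals 5% only at ρ = 1.

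**Is that range of ρ plausible?** A random-intercept, random-slope calculation on the 13 post-baseline visits (Weeks 2 to 108) used assumed slope SDs of 3 to 7 per year, residual SDs of 4 to 10.8 and acute-slope SDs of 10 to 70 per year. It gave ρ of 0.91 to 0.99 and error rates of 5.5% to 7.0%. Settings whose total-slope SD came near the stated 5.50 gave about 5.7% to 7.0%. The calculation assumes complete, balanced data, whereas SAP 8.5.1 uses on-treatment assessments only, so it supports a range and not a point value.

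**Whole procedure, gate passed.** Both hierarchies including Holm were simulated with 2 million draws, taking ρ = 0.95 and other assumed correlations of 0.8 to 0.95. With all five eGFR hypotheses null, the chance of any false claim was 6.5%. In five other null sets it was 6.1% to 6.4%. With total slope effective and the other four null it was 5.0%.

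**Where the rate stays at or below 5%.**

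- Within either hierarchy alone.
- When the surrogate is null: any later false claim needs the gate to be passed, which is itself an error at 0.05.
- When total slope is effective and chronic slope is null: in both hierarchies every false claim first requires the same chronic-slope test to reject.
- When total slope is the only null: both hierarchies use the same p-value, and Holm never tests it above 0.05.

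**The case against.** The strongest reply is that the regional structure is fully disclosed. The text that follows the claim describes country-specific testing, the primary endpoint is defined by region throughout, and no sentence says the trial succeeds if either slope is significant. Each authority judges its own hierarchy, and there 5% holds. This stands as a defence of the design, which is legitimate. It does not rescue the sentence, because neither document limits its claim of overall control to a region.

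Several stronger readings are tempting, and the documents do not support them:

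- *The study-wise rate is about 6%.* Exactly 6.0% needs ρ of about 0.977, which no document supplies, and the figure applies only when the surrogate effect is real.
- *The rate is at most 5% only if every hypothesis is null.* The mixed cases listed in the working contradict this.
- *Testing total slope in both hierarchies inflates error by itself.* Repeating one test on the same data with the same p-value adds nothing.
- *Surrogate real with slopes null is what the sponsor expects.* The same 30-point response difference projects slope differences of 2.52 and 2.1 per year (protocol 12.2.2). The case matters because family-wise control must cover it, not because it is the planning scenario.
- *Any claim not tied to a region should require both slopes.* That would be a new success criterion. It could bar a single study report from stating that one region's primary was met when that hierarchy says it was. No error in the documents requires it.

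**Conclusion.** The error-control claim is wrong as written in the protocol synopsis, protocol 12.10.2 and SAP 8.4. The procedure controls type I error at 2-sided 0.05 within the non-US hierarchy and within the US hierarchy, but not across them. With a real surrogate effect and both slopes null, the chance of at least one false primary claim is above 5% for any correlation below 1. It is 5.7% to 7.0% for assumed correlations of 0.99 to 0.90, with 9.75% as the limit under independence.

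That the rate exceeds 5% in this case follows from the documents alone. Its size rests on bivariate normality and on an assumed correlation. The excess is modest, and neither regional decision is invalid.

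**What to change.** In the protocol synopsis, protocol 12.10.2 and SAP 8.4, replace the study-wide claim with: *type I error is controlled at 2-sided 0.05 separately within the non-US hierarchy and within the US hierarchy; it is not controlled across the two.* Report each primary result as belonging to its own regional hierarchy.

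The cost is a wording amendment and a slightly less favourable stated error property. No test, alpha level or power changes. If the sponsor does want control across the two hierarchies, alpha would have to be shared. Testing each primary at 0.025 would hold the chance of a false primary claim to at most 4.9% (the independent case), but would cut total-slope power from 91.1% to Φ(3.307 − 2.241) = 85.7%. Correcting the sentence does not require that.

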3. LIST OF ABBREVIATIONS AND DEFINITIONS OF TERMS

Abbreviations used throughout the protocol should not be used by the site when documenting adverse events, medical history, etc. on source documents.

Abbreviation	Definition
ACE	Angiotensin-converting enzyme
AE	Adverse event
AEOI	Adverse event of interest
AKI	Acute kidney injury
ALT	Alanine aminotransferase
ANCOVA	Analysis of covariance
AngII	Angiotensin II
ARB	Angiotensin receptor blocker
AST	Aspartate aminotransferase
AT ₁	Angiotensin II type 1 receptor
BMI	Body mass index
CFR	Code of Federal Regulations
CHF	Congestive heart failure
CI	Confidence interval
CKD	Chronic kidney disease
CKD-EPI	Chronic Kidney Disease Epidemiology (equation)
CMH	Cochran-Mantel-Haenszel
COVID-19	Coronavirus disease 2019
DMC	Data Monitoring Committee
DNA	Deoxyribonucleic acid
DUET	Study RET-D-001, NCT01613118, EudraCT 2014-002358-38: Efficacy and Safety of Sparsentan (RE-021), a Dual Endothelin Receptor and Angiotensin Receptor Blocker, in Patients with Focal Segmental Glomerulosclerosis (FSGS): A Randomized, Double-blind, Active-control, Dose-escalation Study
ECG	Electrocardiogram
eCRF	Electronic case report form
EDTA	Ethylenediaminetetraacetic acid
eGFR	Estimated glomerular filtration rate
EM	Electron microscopy
EOS	End of Study
EOT	End of treatment

Abbreviation	Definition
EQ-5D-5L	EuroQol, 5-dimension quality of life instrument, version 5L
EQ-5D-Y	EuroQol, 5-dimension quality of life instrument, version Y
ERA	Endothelin receptor antagonist
ESRD	End-stage renal disease
ET	Early termination
ET _A	Endothelin receptor subtype A
ET _B	Endothelin receptor subtype B
█	█
EU	European Union
FAS	Full Analysis Set
FDA	Food and Drug Administration
FSGS	Focal segmental glomerulosclerosis
GCP	Good Clinical Practice
GFR	Glomerular filtration rate
GMP	Good Manufacturing Practice
HbA1c	Hemoglobin A1c (glycosylated hemoglobin)
HBeAg	Hepatitis B “e” antigen
HBsAg	Hepatitis B surface antigen
HBV	Hepatitis B virus
HCV	Hepatitis C virus
HDL	High-density lipoprotein
HDL-C	High-density lipoprotein cholesterol
HIV	Human immunodeficiency virus
ICF	Informed consent form
ICH	International Council for Harmonisation
IEC	Independent Ethics Committee
IF	Immunofluorescence
INR	International normalized ratio
IRB	Institutional Review Board
IUD	Intrauterine device
IWRS	Interactive web response system
KDIGO	Kidney Disease Improving-Global Outcomes

Abbreviation	Definition
KDQOL	Kidney Disease Quality of Life (instrument)
LDL-C	Low-density lipoprotein cholesterol
LOCF	Last observation carried forward
LS	Least-squares
MCH	Mean corpuscular hemoglobin
MCHC	Mean corpuscular hemoglobin concentration
MCV	Mean corpuscular volume
MedDRA	Medical Dictionary for Regulatory Activities
MI	multiple imputation
MMRM	Mixed Model Repeated Measures
NSAID	Non-steroidal anti-inflammatory drug
OLEFAS	Open-label Extension Full Analysis Set
PedsQL	Pediatrics Quality of Life Inventory
PK	Pharmacokinetic(s)
PP	Per Protocol (analysis set)
PRO	Patient-reported outcome
QoL	Quality of life
RAAS	Renin-angiotensin-aldosterone system
REML	Restricted maximum likelihood
RNA	Ribonucleic acid
RRT	Renal replacement therapy
SAE	Serious adverse event
SAP	Statistical analysis plan
SAS	Statistical Analysis Systems
SD	Standard deviation
SOP	Standard operating procedure
SUSAR	Suspected, unexpected serious adverse reaction
TEAE	Treatment-emergent adverse event
TRPC	Transient receptor potential canonical
UK	United Kingdom
ULN	Upper limit of normal
UP/C	Urine protein/creatinine ratio

Abbreviation	Definition
US	United States
VLDL-C	Very low-density lipoprotein cholesterol
WBC	White blood cell
WHO-DD	World Health Organization Drug Dictionary
WOCBP	Women of childbearing potential

